4.6.7.4. Major Adverse Cardiovascular Events

Death and nonfatal cardiovascular AEs (NCAEs) will be adjudicated by a committee of physicians external to Lilly with cardiology expertise. This committee will be blinded to treatment assignment.

The NCAEs to be adjudicated include

- myocardial infarction
- · cardiogenic shock due to myocardial infarction
- · hospitalization for unstable angina
- · hospitalization for heart failure
- coronary interventions (such as coronary artery bypass graft or percutaneous coronary intervention)
- resuscitated sudden death, and
- cerebrovascular events, including cerebrovascular accident (stroke) and transient ischemic attack.

The counts and percentages of participants with adjudicated NCAEs may be summarized by treatment.

In addition, NCAEs reported by investigator may also be summarized. Death reported by investigator may be listed in a separate table.

A listing of participants reporting NCAEs, either reported by an investigator or identified by the clinical endpoint committee (CEC), will be provided. This listing will include treatment, participant identification including the site number, date of event, type of event as reported by the investigator, type of event as adjudicated by the CEC, time from first dose of study drug to the event, and time from last dose to the event (if participant has discontinued study drug prior to the event).

4.7. Other Analyses

Subgroup analyses of the primary endpoint will be conducted to assess the consistency of the intervention effect across the following subgroups:

- age group: under 65 years versus 65 years and over
- race
- sex: female versus male
- ethnicity
- BMI (kg/m²) group: less than 30 versus 30 or higher, and less than 35 versus 35 or higher
- Visit 1 TG level less than 250 mg/dL versus 250 mg/dL or higher
- Visit 1 TG and LDL-C levels: TG 250 mg/dL or higher and LDL-C 100 mg/dL or higher, versus TG less than 250 mg/dL and LDL-C less than 100 mg/dL, and
- diabetic vs non-diabetic.

For each subgroup analysis, 2 models will be conducted:

- MMRM model: conduct MMRM model as described in Section 4.3.2 on the subgroup only, and
- MMRM model with interactions: the MMRM model as described in Section 4.3.2, adding interactions between subgroup and visit, between subgroup and treatment, and between subgroup, treatment and visit as fixed effects.

Separate MMRMs may be conducted on participants meeting the inclusion/exclusion criteria for the Study EZCB protocol both before and after amendment (e): Visit 1 lipid levels of TG greater than 200 mg/dL and LDL-C greater than 100 mg/dL versus TG greater than 150 mg/dL and LDL greater than 70 mg/dL and non-HDL-C greater than 130 mg/dL. If less than 10% of participants differ between these two subgroups, this analysis will not be produced.

If the number of participants is too small (less than 10%) within a subgroup, then the subgroup categories may be redefined prior to unblinding the study. Additional subgroup analyses may also be performed.

For the purposes of the subgroup analysis, diabetic status will be defined using the criteria described in Appendix 8 (Section 6.8).

Subgroup analyses may be done for the Japanese population to support local regulatory interactions.

4.8. Interim Analyses

A first-planned interim analysis may be conducted when at least 50% of participants complete Day 120 (Visit 7) or discontinue treatment. There may be 2 more interim analyses after the first interim analysis and before final analysis (100% of patients complete 180 days of study or discontinue treatment). These 3 interim analyses will be for the purpose of internal planning and decision making and may assess safety, PK, or efficacy measures.

If an unplanned interim analysis is deemed necessary for reasons other than a safety concern, the Study EZCB protocol must be amended.

An interim assessment committee (IAC) will be formed to review the interim analyses for totality of data including the safety and efficacy reports in an unblinded manner.

The IAC will be fully independent from the study team and will include, at a minimum, a Lilly medical physician and a statistician. Details about IAC membership, purpose, responsibilities, and operation will be described in an IAC charter, which will be approved prior to the first unblinding.

Details on the timing of the interim analyses, operational support, and unblinding will be specified in the IAC charter and in the Study EZCB unblinding plan. Since the endpoints for interim analysis are a subset of the endpoints in Section 1.1, the analysis methods for these endpoints should be consistent with those methods described in this SAP. The time points of at which certain endpoints are assessed may be amended to reflect data availability at the interim. Such changes will be specified in the IAC charter.

Information that may unblind Study EZCB during the analyses will not be reported to study sites or blinded study team members before the study has been unblinded until final database lock. Study sites will receive information about interim results only if deemed necessary for the safety of the participants. Study EZCB will not be stopped based on the superiority of LY3561774 versus placebo. Therefore, there will be no inflation of the type I error rate and no need to employ an alpha spending function or multiplicity adjustment.

4.9. Changes to Protocol-Planned Analyses

The description of the EAS was amended to exclude participants who experienced permanent discontinuation of intervention, initiation of excluded medications taken during the study, and new initiation of any lipid-lowering drug required to be on a stable regimen prior to treatment per the Study EZCB protocol inclusion criteria. In the Study EZCB protocol, the EAS was described as only excluding measurements based on permanent discontinuation of intervention. This change is intended to align the analyses based on the EAS with the description of the primary estimand, based on the hypothetical strategy.

For the exploratory analysis of time-averaged endpoints, the days of time-averaging have been augmented from Day 120 to Day 180 to Day 30 to Day 180, and from Day 210 to Day 270 to Day 120 to Day 270. The purpose of this change is to capture a broader measure of effectiveness over time to accompany our other analyses at specific time points.

5. Sample Size Determination

The sample size calculation is based on the primary efficacy estimand and its endpoint, percent change, from baseline at Day 180 in ApoB.

Approximately 175 participants will be randomly assigned in a 2:1:2:2 ratio to placebo: LY3561774 100 mg:400 mg:800 mg. Assuming a dropout rate, this results in approximately 20 completers for the 100 mg group and 40 completers per arm for the rest of the groups.

Assuming a standard deviation of 15%, and a 2-sided alpha level of 0.05, the completers for each treatment arm will provide greater than 99% power to detect a treatment difference of -30% for the primary endpoint.

6. Supporting Documentation

6.1. Appendix 1: Demographic and Baseline Characteristics

A listing of participant demographics for all randomly assigned participants will be provided. All demographic and baseline clinical characteristics will be summarized by treatment groups for all randomly assigned participants.

Baseline demographic and clinical characteristics of special interest include but are not limited to

- age (years)
- sex (female, male)
- race
- ethnicity
- height (cm)
- weight (kg)
- body mass index (BMI [kg/m²])
- age group (less than 65 years, 65 years or over)
- BMI group (less than 30, 30 or greater and less than 35, 35 or greater)
- LDL-C
- HDL-C
- VLDL-C
- TGs
- ANGPTL3
- non-HDL-C
- ApoB, and
- Visit 1 TG stratum (less than 250 mg/dL, 250 mg/dL or greater).

6.2. Appendix 2: Historical Illnesses and Preexisting Conditions

The count and percentages of participants with historical illnesses and preexisting conditions will be summarized by treatment groups using the MedDRA PTs nested within SOCs. The SOCs will be in alphabetical order. Conditions (that is, PTs) will be ordered by decreasing frequency within the SOC. This will be summarized for all randomly assigned participants.

6.3. Appendix 3: Treatment Compliance

Listing and summary of prematurely discontinuing study treatment (including discontinuation reason) and discontinuing study will be provided by treatment groups.

6.4. Appendix 4: Concomitant Medications

Concomitant medications will be summarized by treatment group. The percentages of participants who took concomitant medication will be summarized by treatment using PTs nested within Anatomical Therapeutic Chemical (ATC) Level 3 codes. The concomitant medications will be ordered by decreasing frequency within each ATC level in the LY3561774 100 mg group.

6.5. Appendix 5: Important Protocol Deviations

Important protocol deviations are identified in the Trial Issues Management Plan. A listing and summary of important protocol deviations by treatment groups will be provided at the end of Study EZCB for all randomly assigned participants.

6.6. Appendix 6: Searching Criteria for Additional Safety Assessments

Hepatic Treatment-Emergent Adverse Events

Treatment-emergent potentially drug-related hepatic disorders will be summarized by treatment using the MedDRA PTs contained in any of the SMQs

- Broad and narrow terms in the Liver-related investigations, signs and symptoms SMQ (20000008)
- Broad and narrow terms in the Cholestasis and jaundice of hepatic origin SMQ (20000009)
- Broad and narrow terms in the Hepatitis non-infections SMQ (20000010)
- Broad and narrow terms in the Hepatic failure, fibrosis and cirrhosis and other liver damage SMQ (20000013), and
- Narrow terms in the Liver-related coagulation and bleeding disturbances SMQ (20000015).

Gallbladder and biliary tract disorders

Treatment-emergent gallbladder and biliary tract disorders will be summarized by treatment using the MedDRA PTs contained in any of the SMQs

- Narrow PTs in Gallbladder related disorders SMQ (20000124)
- Narrow PTs in Biliary tract disorders SMQ (20000125), and
- Narrow PTs in Gallstone related disorders SMQ (20000127).

Injection Site Reactions

Treatment-emergent injection site reactions will be summarized by treatment using the MedDRA PT in any of the following MedDRA HLTs

- Injection site reaction
- Administration site reaction, and
- Infusion site reactions.

Hypersensitivity Events

The hypersensitivity TEAE are characterized as follows

- Anaphylactic reaction SMQ (20000021; narrow, algorithm per SMQ guide, and broad)
- Hypersensitivity SMQ (20000214; narrow and broad)
- Angioedema SMQ (20000024; narrow and broad), and
- Event maps to PT of Injection related reaction (10071152).

Using these four SMQs, the number and percentage of participants who experienced a TEAE for the following will be analyzed for each of the two study intervention time periods (Day 0 to Day 90 and Day 90 to either Day 180 or Day 270 depending on safety follow-up):

- any narrow or algorithmic term from any one of the 4 indicated SMQs (that is, combined search across narrow and algorithmic portions of all 4 SMQs)
- any narrow scope term within each SMQ, separately (that is, narrow SMQ search), and
- any term within each SMQ, separately (that is, broad SMQ search).

6.7. Appendix 7: Clinical Laboratory Evaluation

Table 6.1 Tables and Figures Produced to Support Clinical Laboratory Evaluations

Analysis Type	Analysis Details	Population/Analysis Set
Box plots and mean/SD plots for observed values by visit	Includes participants who have both a baseline and at least 1 postbaseline measurement from a planned visit.	FAS
	Unplanned measurements will be excluded.	
	Last baseline will be used.	
	Original-scale data will be used.	
	Both SI and conventional units will be provided in the axis within a single plot.	
	No inferential statistics.	
	See also: Figure 6.1 from the Analyses and displays Associated with Laboratory Analyte Measurements in Phase 2-4 Clinical Trials and Integrated Submission Documents – Update to Recommendations white paper ^a .	
Box plots and mean/SD plots for change from baseline values by visit	Includes participants who have both a baseline and at least 1 postbaseline measurement from a planned visit.	FAS
by visit	Unplanned measurements will be excluded.	
	Last baseline will be used.	
	No inferential statistics.	
	See also: Figure 6.2 from the Analyses and Displays Associated with Laboratory Analyte Measurements in Phase 2-4 Clinical Trials and Integrated Submission Documents – Update to Recommendations white paper ^a .	
Maximum, minimum, and last observed and change values	Includes all participants who have both a baseline and at least 1 postbaseline measurement.	FAS

Analysis Type	Analysis Details	Population/Analysis Set
	The following will be summarized: o last baseline, last postbaseline, change from last baseline to last postbaseline (last postbaseline minus last baseline) o minimum baseline, minimum postbaseline, change from minimum baseline to the minimum postbaseline (minimum postbaseline minus minimum baseline), and o maximum baseline, maximum postbaseline, change from maximum baseline to the maximum postbaseline (maximum postbaseline minus maximum baseline) P-values using the MMRM or ANCOVA models will be included.	
	See also: Table 6.2 from the Analyses and Displays Associated with Laboratory Analyte Measurements in Phase 2-4 Clinical Trials and Integrated Submission Documents – Update to Recommendations for Labs white paper ^a .	
Participants with elevated or low values meeting specified levels	Excludes analytes collected qualitatively. Definitions provided in Table 59 and 60 from FDA's Standard Safety Tables and Figures Integrated Guide will be used for the numerator ^b . Includes participants with at least 1 postbaseline measurement. For initial controlled analysis sets, maximum baseline is used for elevated assessments and minimum baseline is used for low assessments. For LY-treated analysis sets (all participants receiving at least 1 dose of LY3561774), participants randomly assigned to placebo or active comparator in the initial period, last baseline is used for any change calculations.	FAS
	For controlled analysis sets, statistical comparisons (using methods described in Section 4.3.2) will be included. See Table 24 from FDA's Standard Safety Tables and Figures Integrated Guide (FDA 2022).	
Listing of abnormal laboratory findings	Includes laboratory analytes collected quantitatively (high or low during postbaseline using Level 2 definitions) and qualitatively (abnormal during postbaseline).	FAS

Analysis Type	Analysis Details	Population/Analysis
		Set
	Includes participant identification, treatment group, laboratory analyte collection day (that is, days	
	from start of study intervention), analyte name, and analyte finding.	

Abbreviations: ANCOVA = analysis of covariance; FAS = full analysis set; MMRM = mixed model repeated measures; SD = standard deviation.

- a [PHUSE]. Safety Analytics Working Group. Analyses and displays associated with laboratory analyte measurements in phase 2-4 clinical trials and integrated submission documents update to recommendations. Accessed March 05, 2023. https://phuse.s3.eu-central-1.amazonaws.com/Deliverables/Safety+Analytics/WP068.pdf
- b [FDA] United States Food and Drug Administration. Standard safety tables and figures: integrated guide. August 2022. Accessed May 31, 2023. https://downloads.regulations.gov/FDA-2022-N-1961-0046/attachment_1.pdf

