9.3.5.1. Laboratory Measures and Vital Signs

Laboratory measures and vital signs will be summarized for each scheduled visit by

- actual measures at baseline and postbaseline
- change from baseline to postbaseline, or
- percent change from baseline to postbaseline.

The laboratory measures may be log transformed before statistical analyses, if deemed necessary. Continuous variables, as well as the change from baseline for these variables or other appropriate transformed variables, will be analyzed by MMRM models as described in Section 9.3.1.

The percentages of participants with treatment-emergent abnormal, high, or low measures, including laboratory and vital signs, will be summarized and compared between treatment groups using Fisher's exact test.

The analysis details will be provided in the SAP.

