4.3.2. Main Analytical Approach

Mean percent change of ApoB will be analyzed using the MMRM model for the efficacy estimand. As described in Section 4.1, the response variable will be log-transformed.

A restricted maximum likelihood-based MMRM analysis will be used to analyze continuous longitudinal variables. All longitudinal observations taken at each scheduled postbaseline visit will be included in the analysis. The model for the analysis of the primary efficacy endpoint of percent change from baseline in ApoB will include the fixed class effects of treatment group (placebo, LY3561774 100 mg, LY3561774 400 mg, and LY3561774 800 mg), visit, treatment-by-visit interaction, Visit 1 TG stratum (lower than 250 mg/dL, 250 mg/dL or greater) as well as the continuous baseline value of the log-transformed dependent variable.

An unstructured covariance structure will be used to model the within-participant errors. Significance tests will be based on LS means and type III tests. If this analysis fails to converge, these covariance structures will be tested in order

- Toeplitz with heterogeneity
- autoregressive with heterogeneity
- compound symmetry with heterogeneous variances
- Toeplitz
- · autoregressive, and
- compound symmetry without heterogeneous variances.

The first covariance structure that converges will be used. The Kenward-Roger approximation will be used to estimate denominator degrees of freedom.

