4.5.5. Immunogenicity Assessments

If data from validated immunogenicity assays are available, treatment-emergent-ADAs may be assessed.

Treatment-emergent ADAs are defined as participants

- with a 2-fold (1 dilution) increase in titer than the minimum required dilution if no ADAs were detected at baseline (treatment-induced ADA), or
- with a 4-fold (2 dilutions) increase in titer compared with baseline if ADAs were detected at baseline (treatment-boosted ADA).

The frequency and percentage of participants with preexisting ADA and who are treatment-emergent-ADA positive (TE-ADA+) to LY3561774 will be tabulated.

The distribution of titers and frequency of neutralizing antibodies (if assessed) for the treatment-emergent-ADA+ participants may also be tabulated.

The relationship between the presence of antibodies and PK parameters, efficacy response, or safety to LY3561774 may also be assessed.

4.6. (Other) Safety Analyses

Unless otherwise specified, safety will be assessed by comparing safety of LY3561774 doses with placebo irrespective of adherence to study drug. Thus, safety analyses will be conducted using the SAS.

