4.6.6. Clinical Laboratory Evaluation

All laboratory data will be reported in SI units. Selected laboratory measures will also be reported using conventional units. Limits from the performing lab will be used to define low (L) and high (H). Descriptive summaries by treatment and by nominal visit will be provided for the baseline and postbaseline values, as well as the change from baseline values.

Observed and change from baseline values for each visit may be displayed in plots for participants who have both a baseline and at least 1 postbaseline planned measurement. Baseline will be the last non-missing observation prior to taking the first study drug. Unplanned measurements will be excluded from plots.

A shift table will be provided including unplanned measurements. The shift table will include the number and percentage of participants within each baseline category (low, normal, high, or missing) versus each postbaseline category (low, normal, high, or missing) by treatment. The proportion of participants shifted will be compared between treatments using Fisher's exact test.

For qualitative laboratory analytes, the number and percentage of participants with normal and abnormal values will be summarized by treatment.

A listing of abnormal findings will be created for laboratory analyte measurements, including qualitative measures. The listing will include participant identification, treatment group, laboratory collection date, study day, analyte name, and analyte finding.

Using the SAS, the MMRM model as described in Section 4.3.2 will be used for the analysis during the treatment period for the continuous measurements for selected lab tests. Alternatively, ANCOVA will be used if the MMRM model is not applicable due to unavailability of multiple postbaseline measurements.

Detailed analyses can be found in Appendix 7 (Section 6.7).

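### SAP Table 6.1 sends a yes/no laboratory comparison to the continuous-outcome MMRM of Section 4.3.2, and labels every laboratory row FAS without reconciling that with the safety analysis set

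*SAP*

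**What the plan says.** SAP 6.7 (Appendix 7), Table 6.1, has a row headed "Participants with elevated or low values meeting specified levels". It has a numerator definition taken from an external guide and a denominator of participants with at least one postbaseline measurement. For controlled analysis sets it states that "statistical comparisons (using methods described in Section 4.3.2) will be included". The row also refers to an active comparator, which this trial does not have; the arms are placebo and three LY3561774 doses.

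SAP 4.3.2 is the primary-endpoint section: "Mean percent change of ApoB will be analyzed using the MMRM model for the efficacy estimand". Its general statement is "A restricted maximum likelihood-based MMRM analysis will be used to analyze continuous longitudinal variables".

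Protocol 9.3.5.1 covers the same kind of laboratory outcome: "The percentages of participants with treatment-emergent abnormal, high, or low measures, including laboratory and vital signs, will be summarized and compared between treatment groups", and the sentence ends by naming Fisher's exact test.

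On the analysis set, SAP 4.6 says that "safety analyses will be conducted using the SAS". SAP 4.6.6 adds: "Using the SAS, the MMRM model as described in Section 4.3.2 will be used for the analysis during the treatment period", and then sends the reader to Appendix 7 for detail. All five rows of Table 6.1 are labelled FAS, including the row of maximum, minimum and last values ("Includes all participants who have both a baseline and at least 1 postbaseline measurement"), which carries MMRM or ANCOVA p-values, and the listing of abnormal findings.

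**The concern.** There are two separate problems.

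The first is the method. Whether a participant ever meets a laboratory threshold is a yes/no outcome. A likelihood-based model for log-transformed continuous repeated measures has no such response to fit. A programmer following Table 6.1 literally would have to depart from it, and the departure would be undocumented. The comparison concerned is the between-arm test for notable laboratory abnormalities, for every analyte in the row.

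The second is the data window. The FAS holds treatment-period data only, and the SAS adds safety follow-up. The safety estimand in SAP 1.1 expressly includes follow-up data. Visit 801 collects hematology, chemistry, coagulation and urinalysis, and Protocol 4.2 gives the capture of further safety signals as one purpose of that visit. A FAS label on the abnormal-findings listing leaves those values out of it. SAP 4.6.6 plans a listing of abnormal findings without naming a set, so it would default to the SAS. The two places therefore disagree.

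**Working it through.** The plan states no figure on this point, so the check is mainly a comparison of texts.

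**Method**

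1. Outcome type. The Table 6.1 row is a count of participants over a denominator, so each participant contributes one binary result.
2. Content of SAP 4.3.2. It gives REML estimation, fixed effects for treatment, visit, their interaction and TG stratum, a continuous baseline covariate, an unstructured covariance with fallbacks, and Kenward-Roger degrees of freedom. Nothing in it applies to a proportion.
3. What the other sections say:
   - Protocol 9.3.5.1: Fisher's exact test for percentages with treatment-emergent abnormal, high or low laboratory measures.
   - SAP 4.1: Fisher's exact or Pearson's chi-square test for categorical outcomes other than binary efficacy outcomes.
   - SAP 4.6.6: Fisher's exact test for the laboratory shift table.
4. SAP 4.9 lists two changes to protocol-planned analyses: the EAS definition and the time-averaging windows. Neither concerns this row.
5. Workability of Fisher's test. The planned arms are 175 × 2/7 = 50 for placebo, 400 mg and 800 mg, and 175 × 1/7 = 25 for 100 mg. With an assumed 0/50 on placebo, the two-sided p-values are:
   - against an arm of 50: 0.056 for 5/50 and 0.027 for 6/50;
   - against the 100 mg arm: 0.108 for 2/25 and 0.034 for 3/25.

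   The counts are illustrative. They show only that the test is usable with sparse events at these sizes.

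**Analysis set**

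1. Under SAP 3, the FAS and SAS both contain all randomized participants with at least one dose who were not discontinued for inadvertent enrollment. They differ only in that the SAS adds safety follow-up data. The label changes the observation window, not who is counted.
2. The laboratory MMRM in SAP 4.6.6 is limited to the treatment period, so either label gives it the same data.
3. The label does matter for outputs that could use follow-up values: the elevated/low count, the maximum/minimum/last summary, the by-visit plots and the abnormal listing. Under the FAS these stop at Day 270.
4. Outputs on the SAS, by statement or by default, can still carry Day 360 values: the shift table in SAP 4.6.6, and the liver-injury screening plots, screening tables and participant profiles in Table EZCB.4.5.

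**Who reaches Visit 801**

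The main rule is Day 270 ApoB below 80% of baseline, that is, a change below -20%. The documents give no Day 270 effect. Assume a normal distribution with mean change m and SD 15%, which is the Day 180 planning value in Protocol 9.5. The share is then Φ((-20 - m)/15).

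| Assumed mean change at Day 270 | (-20 - m)/15 | Share with Visit 801 |
|---|---|---|
| 0% | -1.33 | about 9% |
| -10% | -0.67 | about 25% |
| -20% | 0 | 50% |
| -30% | 0.67 | about 75% |

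Attendance therefore depends strongly on response, and the share cannot be narrowed from the documents.

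**The case against.** The strongest reply on method is that this is a wrong section number, not a missing analysis. The right test already stands in Protocol 9.3.5.1 and SAP 4.1, and a competent programmer would use it. That is fair as to effort. A reader might infer that the trial has no valid plan for these comparisons, and the documents do not support that. But Table 6.1 is the operative instruction for this output. It contradicts the protocol, and the conflict should not be left to be settled at programming. The stray active-comparator wording suggests unadapted text; it has no analytic effect of its own.

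On the analysis set, SAP 4.1 and 4.6 both allow exceptions to the SAS rule, as do Protocol 3 and 9.3.1. A table with its own analysis-set column can be read as making one. That stands, but the exception is nowhere explained or listed, and Protocol 9.3.5 states the safety set without a qualifier.

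Three stronger readings are tempting and fail:

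- That all Day 360 laboratory results go unreported. The SAS displays noted above may show them; only Table 6.1 outputs lose them.
- That only participants with suppressed ApoB attend Visit 801. Protocol 7.2 and 8.3.2 also route some discontinuing and pregnant participants to follow-up.
- That most treated participants would attend. This needs a Day 270 effect that the documents do not give, and Protocol 4.3 describes 100 mg as a low-efficacy dose.

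There is also a sound argument for the FAS window in one place. Because Visit 801 attendance depends mainly on ApoB response, including it in a between-arm count would give the arms unequal observation time.

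**Conclusion.** The point holds in two parts of unequal weight.

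The method part is firm. One row of Table 6.1 assigns a binary comparison to a section that contains only a continuous-outcome model, contrary to Protocol 9.3.5.1 and SAP 4.1, and no change is declared. It affects every analyte in that row.

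The analysis-set part is an unreconciled conflict rather than a proven loss of data. Table 6.1 outputs omit Visit 801 values that the safety estimand includes, and the abnormal-findings listing is where this matters most. For the treatment-period MMRM the label makes no difference, and for the between-arm elevated/low comparison the shorter window is the better choice.

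The number of participants concerned is unknown. The range of about 9% to 75% rests on assumed normality, an SD carried over from Day 180, and mean Day 270 changes between 0% and -30%; neither part of the finding depends on it. The primary endpoint is unaffected.

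**What to change.** 1. In the elevated/low row of Table 6.1, replace the reference to Section 4.3.2 with Fisher's exact test, and delete the active-comparator wording.
2. Change the analysis set of the abnormal-findings listing to SAS, so that Day 360 values appear and Table 6.1 agrees with SAP 4.6 and 4.6.6.
3. Keep the between-arm elevated/low comparison on the treatment period, through Day 270. State this in SAP 4.9 as a deliberate exception to the SAS rule, giving response-dependent attendance at Visit 801 as the reason.
4. For each remaining Table 6.1 row, either relabel it SAS or cover it in the same Section 4.9 entry.

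The cost is a few lines of SAP wording and minor table programming. No new data, visits or sample-size work are needed.
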